5.3. Unmasking of the Randomization Codes

The randomization code will be unmasked after all the data queries related to the efficacy and safety outcomes have been resolved and the corresponding data revisions have been completed in the database.

6. ANALYSIS POPULATIONS

The following subject populations will be used for analysis:

The Safety Analysis Group will include all subjects who receive one or more study injections. Data will be analyzed according to the treatment actually received. The safety analyses will be performed on the Safety Analysis Group.

The Efficacy Analysis Group will include all subjects who received injections of the correct dose of study drug medication based on randomization schedule at both Day 0 and Day 14, have the 6-month assessment, and do not have any protocol violations or major deviations. The protocol violations or major deviations will be determined in a blinded

review before database lock. Subjects will be analyzed according to the treatment to which they were randomized. Primary efficacy analyses will be performed on the Efficacy Analysis Group.

The Intent-to-Treat (ITT) Group will include all subjects who were randomized regardless receiving treatment. Subjects will be analyzed according to the treatment to which they were randomized. The ITT group will be used for summarizing the baseline characteristics and for the secondary analyses on the efficacy endpoints.

7. SUBJECT DISPOSITION

Subject disposition information will be summarized for all subjects by dose cohort. Summaries will include the number of subjects:

- enrolled
- in each analysis population
- who received all planned doses of VM202
- who completed each scheduled visit
- who completed the study
- who discontinued the study early, and their primary reason for early discontinuation.

8. DEMOGRAPHIC AND BASELINE CHARACTERISTICS

Demographic and baseline characteristics will be summarized for the Safety Analysis Group, Efficacy Analysis Group and ITT population. Demographic variables include:

- age at informed consent
- sex
- race
- Height
- Weight and BMI

Age, height, weight, and BMI will be compared among treatment groups using the method for continuous variables. Sex and race will be compared among groups using the method for categorical variables.

9. BASELINE VALUES

Unless specified otherwise, the baseline value for each variable is the value recorded at the last visit on or before start of dosing.

10. PRIOR MEDICAL HISTORY

Abnormal medical history will be categorized by body system. The counts and percentages of subjects with medical history within the body system at baseline will be summarized.

11. EFFICACY ANALYSES

The primary efficacy analysis will be based on the Efficacy Analysis Group. Additional efficacy analyses will be performed on the ITT Group.

11.1. Primary Efficacy Analysis

Subjects will be asked to assess the level of pain they feel by selecting a score from 0 (No Pain) to 10 (Worst Possible Pain) in the 7-Day Daily Pain and Sleep Interference Diary 7 days before the Baseline, Day-90, 6-Month, and 9-Month Visits. The average of the pain score will be calculated for each subject at each visit.

The primary efficacy endpoint is the change in average pain score as determined by the 7-Day Daily Pain and Sleep Interference Diary between baseline and the 6-month follow-up. The change in pain will be calculated for each subject as follows:

$$\text{Change} = 6\text{-month Pain Score} - \text{Baseline Pain Score}$$

The baseline pain score is the average of average score at screening and at Day 0. Since higher scores indicate worse pain, a negative value of change means an improvement, and a positive value of change means deterioration.

The mean change in pain will be compared among the three treatment groups. The statistical null and alternative hypotheses for the primary efficacy endpoint are:

$$\begin{aligned} \text{Ho: } \mu_H &= \mu_L = \mu_P \text{ and} \\ \text{Ha: } &\text{at least one of the three } \mu \text{'s is different,} \end{aligned}$$

where μ_H , μ_L , and μ_P are mean change in pain from baseline to 6-month follow-up for VM202 high dose, VM202 low dose, and placebo groups, respectively.

The one-way Analysis of Variance (ANOVA) with treatment (VM202 high dose, VM202 low dose, and placebo) as the factor will be used to compare the mean change in pain among the three treatment groups. Dunnett's test will be used to compare the mean change in pain score between VM202 high dose to placebo and between VM202 low dose to placebo. The 95% confidence interval of the mean pain score difference between VM202 groups and placebo group will be provided.

The mean score and mean score change from baseline to Day-90, and 9 Months will also be summarized using the statistical methods described above.

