SCHEDULE OF EXAMINATIONS	Screening (Day -60 to Day 0) Day 0 Day 14 ± 1 days Day 21 ± 3 days Day 30 ± 3 days Day 60 ± 3 days Day 90 ± 7 days Month 6 ± 1 month Month 9 ± 1 month
STUDY ENDPOINTS	The primary study endpoint is the change in the average 24 hour pain score (change from baseline to the 6-month follow-up). The difference in the mean of the change in the average 24-hour pain score will be compared between the treatment groups and the placebo arm to determine the treatment effect. The average pain scores will be obtained from the Daily Pain and Sleep Interference Diary (recorded daily by the patient for 7 days during Screening prior to the first round of injections and again, before the 6 month follow-up).
SAFETY	Any subject who receives study drug (VM202 or placebo) will be included in the safety analysis population. Adverse events (including serious adverse events, and adverse events leading to treatment discontinuation) throughout the 9 months follow-up will be described according to severity and to their relationship with the study drug and injection procedure. Descriptive statistics (N, mean, median, SD, minimum and maximum values, where applicable) will be used to characterize safety parameters.
	All subjects will undergo testing as presented in the American Cancer Society Cancer Screening Guidelines as part of their baseline testing to rule out cancer.
PHARMACOKINETICS	Determination of HGF serum levels will be determined immediately pre-treatment on Day 0, immediately pre-treatment on Day 14, on Day 30, Day 60, and Day 90. The number of copies of VM202 in whole blood will be determined at Day 0 (pre-injection, and 2 hours [± 1 hour] post injection), at Day 14 (pre-injection, and 2 hours [± 1 hour] post injection), Day 21, Day 30, Day 60 and Day 90.
OTHER EFFICACY MEASURES	The 24 hour average pain score obtained from the Daily Pain and Sleep Interference Diary will be compared at all other study visits,

as will the Brief Pain Inventory for Diabetic Peripheral Neuropathy (BPI-DPN), the VAS score obtained during follow-up visits, symptoms of the Brief Peripheral Neuropathy Screening (BPNS), the Patients' Global Impression of Change (PGIC), MNSI, and histological findings on skin biopsy.

TABLE OF CONTENTS

INVESTIGATOR'S AGREEMENT.....	2
STUDY SYNOPSIS	3
TABLE OF CONTENTS	10
ABBREVIATIONS	14
PERSONNEL AND FACILITIES.....	15
1. BACKGROUND.....	16
1.1. Diabetes	16
1.1.1. Diabetic Peripheral Neuropathy	16

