3.2. STUDY DESIGN

This is a phase II, double-blind, randomized, placebo-controlled, multicenter, 9-month study designed to assess the safety and efficacy of VM202 in subjects with painful DPN. Subjects with painful DPN will be screened for study eligibility after giving informed consent.

Initial Screening Activities. Prior to full screening, subjects will give informed consent and then be initially screened using the VAS, the Symptoms portion of the BPNS and the MNSI. Only subjects with a VAS score of ≥ 40 mm, a ≤ 5 point difference in symptom of BPNS between legs and MNSI score of ≥ 3 will be allowed to proceed with the full screening procedures. ***Screening.*** If the VAS, BPNS and MNSI criteria are met, the rest of screening will proceed. If applicable, the subject will be washed out of prohibited medications. During medication wash-out, screening procedures consisting of assessment of study eligibility, a complete medical history, vital signs, physical exam, concomitant medications, cancer screening tests, viral screening, 12 lead EKG, retinal fundoscopy, serum chemistry

and hematology including HbA1c, urinalysis, and pregnancy test (women of childbearing potential only).

If applicable, the subject will be washed out of prohibited medications 14 days prior to initiation of the 7 day Daily Pain and Sleep Interference Diary. The Daily Pain and Sleep Interference Diary shall be completed with 14 days of the first injections. Subjects will be asked to rate their 24-hour average daily pain intensity score using an 11 point numerical scale with 0 = no pain – 10 =worst pain possible, and to evaluate how much their pain interferes with sleep (also an 11 point numerical rating scale from 0 (did not interfere with sleep) to 10 (completely interfered with sleep; patient was not able to sleep due to pain). The subject must record at least five assessments of the 24-hour average daily pain intensity score during the seven-day period. The mean baseline 24-hour will represent the baseline reference value. The average daily pain intensity score of the Daily Pain and Sleep Interference Diary must be ≥ 4 with a standard deviation ≤ 2 in order to be eligible for study participation.

[figure not shown]
Data from the Daily Pain and Sleep Interference Diary at screening and BPI-DPN on Day 0 will represent the baseline reference values.

All screening assessments should occur within the 60 days prior to Day 0 (day of first injections).

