- ***Following medication washout (if applicable) and within 14 days prior to injection.*** Subjects will keep a Daily Pain and Sleep Interference Diary for 7 days. They will be asked to rate their 24-hour average daily pain intensity score using an 11 point numerical scale with 0 mm = no pain – 10 0 mmworst possible pain, and to evaluate how much their pain interferes with sleep (also using an 11 point numerical rating scale from 0 (did not interfere with sleep) to 10 (completely interfered with sleep; patient was not able to sleep due to pain). The subject must record at least five assessments of the 24-hour average daily pain intensity score during the seven-day period. The mean 24-hour scores at Screening will represent the baseline reference value. In case less than five assessments are recorded, a new Daily Pain and Sleep Interference Diary will be provided and the Day 0 visit will be rescheduled to allow completion of the Diary. The average pain score of the Daily Pain and Sleep Interference Diary must be ≥ 4 with a standard deviation ≤ 2 in order to be eligible for study participation.

[†] subjects can participate in the study if PSA is elevated, but cancer can be excluded

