6.3.1. PRIMARY ENDPOINT

The primary study endpoint is the change in average 24-hour pain score from baseline to the 6-month follow-up. The average pain scores will be obtained from the Daily Pain and Sleep Interference Diary (recorded daily by the patient for 7 days prior to the first round of injections and again, for 7 days before the 6 month follow-up). The difference in the mean change in average 24 hour pain score between the two treatment groups and the placebo arm will be evaluated to determine the treatment effect.

The primary analysis will be conducted in the Efficacy Analysis Group. A secondary analysis will be conducted in the ITT group, and further analyses conducted as necessary to explore any inconsistency between the two results.

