11.1.1. Handling Missing Data

For ITT population, the analyses with imputation for missing data will be performed for the primary efficacy endpoint (pain score change from baseline to 6 months). For subjects without the primary efficacy endpoint, the following imputation methods will be considered:

- For subjects with an early drop-out reason not related to death or AEs, the last available value (LOCF) of the subject will be used for the missing 6-month value. For early discontinued subjects due to AEs, the maximum value of all available 6-month pain score will be imputed for the missing 6-month value. For early discontinued subjects due to death, no imputation will be performed and therefore will not be included in the 6-month analyses if they are discontinued prior to the 6-month visit.

No imputation for missing values will be performed for other variables.

11.2. Outcome of at least 50% Reduction in Average Pain Score from Baseline to 6-Month

The percent reduction in the average pain score (determined by the 7-Day Daily Pain and Sleep Interference Diary) from baseline to 6-month follow-up will be calculated for each subject as follows:

$$\% \text{ reduction} = (\text{Baseline Pain Score} - \text{6-month Pain Score}) \div \text{Baseline Pain Score} \times 100\%.$$

The percentage of subjects with at least 50% reduction in pain from baseline to the 6-month follow-up and the corresponding 95% confidence intervals based on the binomial distribution will be calculated for each study group. Fisher's exact test will be used to compare the percentage of subjects with at least 50% reduction in pain among the three study groups. The comparison between the placebo group and each of the two VM202 group will also be performed by Fisher's exact test. The 95% confidence interval of the difference between placebo and each of the two VM202 group in the percentage of subjects with at least 50% reduction will be derived by the two-sample normal distribution.

The percentage of subjects with at least 20%, 30%, 40%, 60%, 70%, and 80% reduction in pain and the corresponding 95% confidence intervals based on the binomial distribution will also be provided.

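### The primary baseline in SAP 11.1 averages in a Day 0 diary score that neither document collects, and it contradicts the protocol's own baseline

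*SAP*

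**What the plan says.** The primary endpoint is the change in average diary pain score from baseline to 6 months. SAP 11.1 states the baseline rule: "The baseline pain score is the average of average score at screening and at Day 0". The same section says the diary is kept "in the 7-Day Daily Pain and Sleep Interference Diary 7 days before the Baseline, Day-90, 6-Month, and 9-Month Visits", which is one diary before treatment and three after it.

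The protocol defines the diary baseline without a Day 0 component:

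- Synopsis, Study Endpoints: the baseline scores are "recorded daily by the patient for 7 days during Screening prior to the first round of injections".
- Section 6.3.1: they are "recorded daily by the patient for 7 days prior to the first round of injections".
- Section 3.4.3: "The mean 24-hour scores at Screening will represent the baseline reference value".
- Section 3.2 separates the instruments: "Data from the Daily Pain and Sleep Interference Diary at screening and BPI-DPN on Day 0 will represent the baseline reference values".

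The SAP also has a general rule in section 9: "Unless specified otherwise, the baseline value for each variable is the value recorded at the last visit on or before start of dosing". Its list of definitions likewise takes the latest available value before dosing starts.

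**The concern.** The rule calls for two diary averages before treatment, and the schedules supply one. An analyst who follows SAP 11.1 literally cannot compute the primary endpoint, and one who computes it must depart from the text.

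The sentence also sets the baseline for the Day 90 and 9-month pain changes. In SAP 11.2 baseline enters the responder rates twice, in the numerator and as the denominator. The study is meant to supply effect sizes and variability for a pivotal trial (SAP section 4), so the definition of the primary change score matters even though SAP sections 5 and 5.2 treat p-values as descriptive.

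There is also some risk that the gap is filled with the wrong instrument. A VAS is taken at Day 0, and the titles of Tables 5.1 to 5.3 in SAP Appendix A label the diary output as a visual analogue scale.

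**Working it through.** **The plan's own figure.** SAP section 4 gives power of 80%, 70% and 60% for differences of 21.5, 19.5 and 17.5 mm (40 versus 20 subjects, SD 25 mm, two-sided alpha 0.025). The standard error is 25 × √(1/40 + 1/20) = 6.85 mm, so the noncentrality parameters are 3.14, 2.85 and 2.56. The noncentral t distribution with 58 degrees of freedom gives 79.7%, 70.7% and 60.2%. The figures reproduce. They do not use the baseline definition, so this point leaves them unchanged.

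**Diary averages before dosing: required and collected.**

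| Source | Diary before dosing |
|---|---|
| SAP 11.1, baseline rule | Two: screening and Day 0 |
| SAP 11.1, collection points | One: Baseline |
| SAP Table 2 | One: Screening; Day 0 blank |
| Protocol Appendix 1 | One: Screening; Day 0 blank |
| Protocol 3.4.8.1, Day 0 pre-injection list | None; the pain measures are VAS and BPI-DPN |
| Protocol 4.2.8 | One: Screening, after washout |

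Required: 2. Collected: 1.

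**Can another provision supply the second value?**

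- *The Day -7 entry (Protocol 3.4.7).* It fits the timing of the same 7-day diary, which Protocol 3.4.3 places within 14 days before injection. If Day 0 in the SAP meant this diary, the rule would average one value with itself.
- *The repeat diary (Protocol 3.4.3).* It is issued when fewer than five days were recorded. It is not a second baseline.
- *The Day 0 VAS.* SAP 11.3.1 states that the VAS analysis is separate from the diary. VAS is in fact collected at both screening and Day 0, and its averaging rule has a fallback when one value is missing. The diary rule has none.
- *SAP section 9.* It yields to any specific rule, and 11.1 is one.
- *SAP 11.1.1.* It imputes only the 6-month value, and then: "No imputation for missing values will be performed for other variables".

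**Reach.** Change scores using this baseline: Day 90, 6 months and 9 months, which is 3. Responder thresholds in SAP 11.2: 20, 30, 40, 50, 60, 70 and 80%, which is 7.

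**What a wrong substitution would do (assumed values, for illustration only).** Take a diary mean of 6.0 and a 6-month mean of 3.0. The protocol baseline gives a change of 3.0 − 6.0 = −3.0 and a reduction of 3.0/6.0 = 50.0%. If a Day 0 score x from another instrument, put on the 0 to 10 scale, were averaged in, baseline would be (6.0 + x)/2:

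- x = 4: baseline 5.0, change −2.0, reduction 40.0%
- x = 8: baseline 7.0, change −4.0, reduction 57.1%

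The same subject falls on either side of the 50% cut.

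**One diary or two (assumption: equal variances and equal correlation ρ).** With one baseline diary, the variance of change is 2(1 − ρ)σ². With two averaged, it is [1 + (1 + ρ)/2 − 2ρ]σ² = 1.5(1 − ρ)σ². The ratio of SDs is √0.75 = 0.866 at any ρ. The two definitions are therefore not interchangeable for estimating variability, but only the first can be computed here.

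**The case against.** The strongest reply is that this is a drafting slip with one evident meaning. The endpoint is explicitly the diary score, and only one diary precedes dosing. Dropping the absent term, averaging whatever exists, or following the protocol all give the same number. The SAP's list of definitions contains a workable baseline that returns the screening diary mean. No sensible analyst would discard all 100 subjects, since eligibility itself depends on that diary. SAP section 1 already requires departures to be documented in the study report.

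Much of this stands. The intended value can be recovered, no data are lost, and the none-of-100 figure is a consequence of literal reading, not a forecast. It does not remove the error. A general definition gives way to the specific rule for the primary endpoint, and a latest-value definition itself disagrees with averaging. Relying on a reported deviation means settling the primary baseline outside the plan.

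Two smaller objections concern the Day -7 entry and the replacement text. The Day -7 entry follows the treatment authorization and randomization sections, which leaves some room to imagine a second diary. But Protocol 3.4.5 requires the completed diary before authorization, and Protocol 4.2.8 and Appendix 1 list one. The replacement text leaves two cases open: a subject given a second diary, and a randomized subject admitted with fewer than five entries. Both are fair points and are taken up in the fix.

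**Conclusion.** The concern holds. The baseline sentence in SAP 11.1 needs two diary averages where one is collected, cannot be carried out as written, and contradicts Protocol 3.2, 3.4.3 and 6.3.1. It affects three change scores, including the primary one, and seven responder rates. Read literally, 0 of 100 planned subjects have a baseline pain score; with the Day 0 term removed, every subject with a qualifying screening diary has one. The stated power is unaffected.

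This is an error in the stated rule, not a loss of data, and it should be corrected before the codes are opened. The conclusion rests on the schedules and text alone. The 40.0% to 57.1% range and the 0.866 ratio are illustrations under stated assumptions and are not needed for it. The wording may have been carried over from the VAS rule in SAP 11.3.1, but that is inference.

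**What to change.** In SAP 11.1, delete the Day 0 term and replace the sentence with:

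> The baseline pain score is the mean of the recorded 24-hour average pain scores (at least five of seven) from the single 7-day diary completed at Screening, after any washout and within 14 days before the first injections.

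The sponsor should confirm that no second pre-dose diary was intended and make the change before unmasking (SAP 5.3). Two short clauses would complete it: where a repeat diary was issued, say which diary counts; and say how a randomized subject with fewer than five entries is handled in the ITT analysis. Retitling Tables 5.1 to 5.3 so that they no longer call the diary a visual analogue scale would remove the remaining ambiguity.

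The essential change costs one sentence in the SAP. Data collection, sample size and other endpoints stay as they are.

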19. Major psychiatric disorder within last 6 months that would interfere with study participation;
20. Body mass index (BMI) $> 45 \text{ kg/m}^2$ at Screening;
21. Any lower extremity amputation;
22. Use of an investigational drug or treatment in past 6 months; and
23. Unable or unwilling to give informed consent.

STUDY PROCEDURES

Screening should occur within the 60 days prior to Day 0 (day of injection) and assessments other than the completion of the Diary may be scheduled during medication washout. Screening will include assessment of study eligibility, a complete medical history, vital signs, physical exam, concomitant medications, cancer screening tests, viral screening, MNSI, VAS, 12 lead EKG, retinal fundoscopy, serum chemistry and hematology, and pregnancy test (women of childbearing potential only).

Prior to full screening, subjects will give informed consent and then be initially screened using the VAS, the Symptoms portion of

the BPNS and the MNSI. Only subjects with a VAS score of ≥ 40 mm, a ≤ 5 point difference in symptom of BPNS between legs and MNSI score of ≥ 3 will be allowed to proceed with the full screening procedures. The remaining screening activities will include assessment of the other study eligibility criteria, a complete medical history, vital signs, physical exam, concomitant medications, cancer screening tests, viral screening, 12 lead EKG, retinal fundoscopy, serum chemistry and hematology including HbA1c, urinalysis, and pregnancy test (women of childbearing potential only).

If applicable, the subject will be washed out of prohibited medications prior to initiation of the 7 day Daily Pain and Sleep Interference Diary; completion of the Diary should occur within 14 days prior to the first round of injections. The average pain score of the Daily Pain and Sleep Interference Diary must be ≥ 4 with a standard deviation ≤ 2 in order to be eligible for study participation.

Eligible subjects will be randomly assigned in 2:2:1 ratio to the low dose, high dose or placebo group.

Prior to injections, subjects will undergo a skin biopsy (one 3 mm diameter round sample from the left ankle, the left calf and the left upper thigh, for a total of 3 samples / subject). Subjects will receive VM202 or placebo (normal saline) by intramuscular injections in both legs (in the calf) on Day 0, and Day 14 as follows:

TREATMENT GROUP	DOSE VM202 (mg) / VISIT / LEG		FINAL DOSE VM202 / LEG (mg)	FINAL DOSE VM202 / PATIENT (mg)
	DAY 0	DAY 14		

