4. SAMPLE SIZE JUSTIFICATION

The sample size for this Phase 2 study was chosen to estimate effect sizes and variability for a pivotal study. Based on the 12 subjects in the Phase I study (Protocol VMDN-001), the overall mean VAS reduction from baseline to 6 months is about 23 mm with a standard deviation of about 25 mm.

This Phase II study has two VM202 dose groups (16 mg and 32 mg) and a placebo group. The study goal is to identify any difference in mean reduction in pain as measured by the Daily Pain and Sleep Interference Diary between each of the two VM202 groups against the placebo group. Based on the two-sided two-sample t-test with a significance level of 0.025 (per the Bonferroni adjustment for multiple comparisons) and an assumption of a standard deviation of 25 mm, a sample size of 40 subjects versus 20 subjects has a statistical power of 80% to detect a mean difference of 21.5 mm, a statistical power of 70% to detect a mean difference 19.5 mm, and a statistical power of 60% to detect a mean difference of 17.5 mm. Therefore, the sample size for Protocol VMDN-002 is determined to be 40 subjects in the VM202 16 mg group, 40 subjects in the VM202 32 mg group, and 20 subjects in the placebo group.

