5.2. Statistical Methods

Although the detectable effect size for the mean pain score reduction is calculated by the two-sided t-test with a significance level of 0.025 per Bonferroni adjustment, the Analysis of Variance (ANOVA) will be performed to detect any difference in the 6-month mean pain score reduction (as measured using the Daily Pain and Sleep Interference Diary) among the three study groups first and, if there is a significant findings based on ANOVA,

the Dunnett's test for the multiple comparisons will be used to compare each of the two VM202 groups and the placebo group in the 6-month mean pain score. Therefore, two-sided p-values <0.05 will be considered statistically significant, unless otherwise stated. As described previously, regardless of the statistical significance, the p-values of the statistical tests should be used descriptively with clinically meaningful interpretation.

Separate statistical tests will be performed at each time point for key endpoints of interest such as Visual Analogue Scale for Pain, Brief Pain Inventory for Diabetic Peripheral Neuropathy, Michigan Neuropathy Screening Instrument, Patients' Global Impression Change, and the [REDACTED] No adjustment for multiplicity will be performed.

In general, an overall test to determine if there is a statistically significant difference among the three treatment arms will be conducted first. Further comparisons will be made to determine if either the low or high dose groups are statistically significantly different from the placebo group.

For continuous variables, a one-way analysis of variance (ANOVA) with treatment group (high dose, low dose, and placebo) as a factor will be used to determine if there is a significant difference among the groups. The low and high dose groups will each be compared against the placebo group using Dunnett's test. The mean difference between the VM202 groups versus placebo along with 95% confidence intervals for the mean difference will also be presented.

For categorical variables, Fisher's exact test will be used to determine if there is a significant difference among the three treatment groups. Separate Fisher's exact tests will be used to compare the low and high dose groups to the placebo group.

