11.3.4. PATIENTS' GLOBAL IMPRESSION OF CHANGE (PGIC)

Subjects will be asked to assess the level of the change of their overall status since the start of the study (scale of 1 to 7) at Day-30, Day-60, Day-90, 6-Month, and 9-Month Visits. PGIC score will be summarized by study visit and treatment arm using the method for continuous variables.

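### The primary ANOVA on change has no baseline term; adding baseline diary pain as a covariate would gain modest precision at almost no cost

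*SAP*

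**What the plan says.** SAP 5.2 sets the rule for every continuous variable: "a one-way analysis of variance (ANOVA) with treatment group (high dose, low dose, and placebo) as a factor". SAP 11.1 applies it to the primary endpoint, 6-month diary mean minus baseline diary mean: "The one-way Analysis of Variance (ANOVA) with treatment (VM202 high dose, VM202 low dose, and placebo) as the factor will be used". Dunnett comparisons of each dose with placebo follow. Protocol 6.3.1 compares mean change and names no covariate.

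Neither document contains a baseline covariate, a baseline-adjusted sensitivity analysis or stratification by baseline pain. Under Protocol 3.4.6 kits are shipped in sequence. Baseline pain is not among the characteristics that SAP 8 compares between arms.

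Three further statements bear on the point:

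- SAP 4 gives the purpose of the sample size: "The sample size for this Phase 2 study was chosen to estimate effect sizes and variability for a pivotal study".
- The screening diary mean "must be ≥ 4 with a standard deviation ≤ 2 in order to be eligible for study participation" (Protocol synopsis, 3.2 and 3.4.3), which limits the spread of the baseline.
- The baseline is not defined consistently. SAP 11.1 has "The baseline pain score is the average of average score at screening and at Day 0"; Protocol 3.4.3 has "The mean 24-hour scores at Screening will represent the baseline reference value". The SAP's definitions table and Section 9 use the last value before dosing, and no Day 0 diary is scheduled.

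**The concern.** An ANOVA on change is an ANCOVA with the baseline slope held at 1. If 6-month pain follows baseline pain less steeply than that, part of the spread in the change scores is predictable from baseline, yet the planned model leaves it in the error term. In any one trial, a chance difference in baseline pain between arms then enters the estimated effect as (slope − 1) × imbalance.

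This matters more than usual for two reasons. Placebo has only 20 subjects and serves both comparisons. The trial is also meant to supply an effect estimate and a variability figure for a pivotal study, and the plan reports no baseline-adjusted version of either. At stake are the width of the interval and the usefulness of the planning figures, not the validity of the result.

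**Working it through.** **1. The plan's own power.** Inputs from SAP 4: 40 versus 20 subjects, SD 25 mm, two-sided alpha 0.025.

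- SE = 25 × √(1/40 + 1/20) = 25 × 0.274 = 6.85 mm.
- At 21.5 mm the noncentrality is 21.5 / 6.85 = 3.14 on 58 degrees of freedom, and the power is 79.7%.
- At 19.5 and 17.5 mm it is 70.7% and 60.2%.

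The SAP states 80%, 70% and 60%, so its figures reproduce without adjustment.

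**2. What the covariate removes.** Let 6-month pain = constant + treatment effect + β × baseline + residual. Then change = constant + treatment effect + (β − 1) × baseline + residual, and

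fraction of variance removed = (1 − β)² × SD_baseline² / SD_change².

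**3. Assumptions.** The documents give neither β nor the diary's baseline SD. I take 10 mm as 1 diary point, so the change SD is 2.5 and the planning difference 2.15. The central case is baseline SD 1.5 and β = 0.5. This implies a residual variance of 6.25 − 0.25 × 2.25 = 5.69, a follow-up SD of √(0.25 × 2.25 + 5.69) = 2.5 and a correlation of 0.5 × 1.5 / 2.5 = 0.3.

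**4. Central case.**

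- Variance removed: 0.25 × 2.25 / 6.25 = 9%.
- Power by the SAP's t-test formula at 21.5 mm: 79.7% to 83.6%, before charging for the extra term.
- Shift from a one-SE baseline imbalance: 0.5 × 1.5 × 0.274 = 0.21 points. This is 10% of 2.15 and 0.3 of the SE (2.5 × 0.274 = 0.68). It is the same effect seen another way, since 0.3² = 0.09, and not a second loss.

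**5. Range.**

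- Baseline SD 1.0 to 1.73, where 1.73 = 6/√12 is a flat spread over the permitted 4 to 10, with β from 0.5 to 1: 0 to 12% removed, power 79.7% to 84.9%.
- Baseline SD at 0.6 of the follow-up SD, correlation 0.2 to 0.7: 0 to 14%, power about 80% to 86%.
- Equal baseline and follow-up SDs would give (1 − r)/2, or 35% to 15% for r = 0.3 to 0.7. With the change SD held at 2.5, however, this needs a baseline SD of 2.5/√(2(1 − r)) = 2.1 to 3.2 points, which is hard to reconcile with a baseline confined to 4 to 10. I do not rely on it.
- If the diary's change SD is below 2.5, the fraction rises. At 2.0 the central case gives 0.5625 / 4.0 = 14%.

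**6. Simulation of the three-arm analysis.** 40,000 trials per setting, arms 40/40/20, baseline truncated to 4–10 with SD 1.5, difference 2.15, Dunnett two-sided 5% critical value 2.22.

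| True slope | Power, ANOVA | Power, ANCOVA |
|---|---|---|
| 0.5 | 81.8% | 85.1% |
| 0.75 | 82.2% | 82.7% |
| 1 | 82.2% | 81.8% |

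At slope 0.5 the mean interval width is 3.03 points for ANOVA and 2.91 for ANCOVA, and both estimators are unbiased (mean −2.147). Under the null, the rejection rate per comparison is 3.0% and 3.2%. Requiring a significant overall ANOVA first, as SAP 5.2 does, gives 80.4% and 83.4% at slope 0.5 in a separate simulation.

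**7. Cost if the slope is exactly 1.** By formula, charging one degree of freedom and the expected covariate imbalance, power goes from 79.7% to 78.9% in a 60-subject comparison. With the error variance pooled over 100 subjects it goes from 80.5% to 80.0%.

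**The case against.** The strongest reply is that nothing is wrong. ANOVA on change is a recognised, unbiased choice, the stated power is correct for it, and SAP 5 and 5.2 say that p-values are descriptive. A gain of 3 or 4 power points then has little consequence, and in the central case the interval narrows by only 0.12 points, or 4%. The benefit also rests on an assumed slope of 0.5; at 0.75 it nearly disappears. All of this is true, and it is why the point is an improvement and not an error. Descriptive p-values do not remove it, though: they put more weight on the estimate and its interval, which is what the covariate sharpens.

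Two narrower objections stand in part.

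- The 79.7% to 83.6% comparison is for a two-group t-test, not the SAP's gated procedure. The gated simulation shows a similar gain of about 3 points.
- A residual SD could be worked out from the SDs of baseline, 6-month score and change, if these are tabulated by arm on the same subjects. That reduces the planning benefit, but it does not give a baseline-adjusted treatment estimate or interval.

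The conflict over the baseline definition is a separate problem. The change score needs it resolved with or without a covariate. Finally, no gain has been calculated for the secondary scales.

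**Conclusion.** The point holds as a worthwhile, low-cost improvement. The primary model has treatment as its only term, and neither document adjusts for baseline anywhere. The missing term and its small cost are certain. The gain is modest and depends on assumption: about 9% of the variance and 3 points of power at slope 0.5 with baseline SD 1.5, 0 to 14% over the ranges relied on, and a loss of about half a point of power if the slope is 1. These figures also rest on carrying the SAP's 25 mm, which comes from VAS change in 12 Phase I subjects, over to the diary mean. No conclusion of the current plan is invalidated.

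**What to change.** - Settle one baseline definition for the diary in SAP 11.1, consistent with the protocol and with the diaries actually scheduled, and use it for both the change score and the covariate.
- Make the primary model an ANCOVA of 6-month change, with treatment as factor and the baseline diary mean as covariate.
- Report Dunnett-adjusted differences in adjusted means with 95% confidence intervals, together with the residual SD and the estimated slope for pivotal planning.
- Keep the unadjusted one-way ANOVA as a sensitivity analysis.
- For consistency, use the same model with each scale's own baseline for VAS, BPI-DPN, MNSI and sleep interference. Leave PGIC as it is ("PGIC score will be summarized by study visit and treatment arm using the method for continuous variables"): it is itself a rating of change and has no baseline.

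The cost is one model term, a line or so of SAP wording and one error degree of freedom. No new data are needed. The change should be made before the randomisation code is unmasked.
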